1 BACKGROUND

In the NHS, each year around 2100 infants (3/1000 live births) undergo cooling therapy to reduce brain injury following exposure to lack of oxygen and blood supply to the whole body around the time of birth⁴. This condition is called hypoxic-ischemic encephalopathy (HIE) and cooling therapy is the current standard treatment⁵ for infants with HIE. The cooling therapy involves cooling the whole body with a blanket or wrap that contains cold or warm water circulating through it and covering the baby's body. During cooling therapy, body temperature is maintained at 33-34°C for three days followed by 6-8 hours of rewarming to normal temperature of 36.5°C⁶. Most of the cooled infants often need intensive care including support for breathing, heart function and monitoring of brain activity including identifying and treating seizures⁶. As cooling therapy needs to be delivered in tertiary neonatal intensive care units (NICUs)⁵, babies with HIE born in peripheral hospitals will be transferred to tertiary NICU soon after birth and mothers who will be recovering from the delivery typically arrive a day later to the tertiary NICU. On arrival, parents often receive the news that their baby may die or suffer brain damage⁷. Furthermore, our national survey of neonatal intensive care units (NICU) offering cooling therapy showed that 95% of units do not allow parents to cuddle their babies during the entire cooling therapy period due to concerns of destabilising the cooling process and intensive care⁸. This practice has been reported to compromise parent-infant bonding by 80% of mothers in a recent cross-sectional survey⁹. The physical separation ensuing from transferring the baby to a distant NICU offering cooling therapy and the lack of emotional support after receiving the news that their baby may die or suffer brain damage further impedes the development of parent-infant bonding¹⁰. Impaired parent-infant bonding affects the establishment of breastfeeding¹¹, leads to emotional neglect in the newborn period¹², influences the emotional and cognitive development of children¹³, and results in postnatal stress or depression in parents^{14,15}, which if persistent may lead to behavioural problems in childhood^{16,17}. Given that the survivors of cooling therapy are already at a higher risk of neurodevelopmental disability with 22% having disability at 18 months¹⁸, and 18-20% having cerebral palsy^{19,20}and 30-40% having intellectual disabilities at school-age^{21,22}, compromised parent-infant bonding might contribute to or worsen the outcome in these vulnerable infants.

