5.1.1.5 Stop rules for the cuddle

Cuddle will be stopped, and the baby transferred back to the cot, if any of the following occurs continuously for 5 to10 minutes during cooling without responding to any potential resolvable causes:

- 1. Rectal temperature < 30.0°C or >35.0°C
- 2. Mean blood pressure < 30mmHg or > 75 mmHg
- 3. Heart rate < 50 beats per minute
- 4. Heart rate >180 beats per minute
- 5. Oxygen saturation < 80%
- 6. Fraction of inspired oxygen >70%
- 7. Electroclinical or electrical status epilepticus

If any of the following occurs for greater than 20 minutes after any remediable causes are attended to:

- Rectal temperature between 30.0 and 32.9°C or between 34.1 and 34.9°C
- Mean blood pressure 10 mmHg below or above the pre-cuddle period
- Heart rate <20 beats per minute from the pre-Cuddle period or >20 beats per minute from the pre-Cuddle period
- Oxygen Saturation 80-88%
- Increase in Fraction of inspired oxygen by 20% above the pre-CoolCuddle period

or

• Medical or nursing concern that the infant is not adequately supported

If cuddle is undertaken during the rewarming period, the following stop rules will apply if they occur continuously for 5 to 10 mins despite attending to the potentially remediable actions:

- 1. Mean blood pressure < 30 mmHg or > 75 mmHg
- 2. Heart rate < 50 beats per minute
- 3. Heart rate > 180 beats per minute
- 4. Oxygen saturation < 80%
- 5. Fraction of inspired oxygen >70%
- 6. Electroclinical or electrical status epilepticus

The following stop rules will apply during the rewarming period, if they persist for greater than 20 minutes after any remediable causes are attended to:

- Rectal temperature greater than 4.0°C or less than 4.0°C from the pre-CoolCuddle period
- Heart rate 30 beats per min above or below the pre-CoolCuddle period
- Mean Blood pressure 20mmHg above or below the pre-CoolCuddle period
- Oxygen saturation 80-88% below the pre-CoolCuddle period
- Increase in Fraction of inspired oxygen by 20% above the pre-CoolCuddle period

Or

Medical or nursing concern that the infant is not adequately supported

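### The rewarming oxygen-saturation stop rule is mis-worded: read like its neighbours it can never act before the below-80% rule, and at best it is ambiguous

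*Protocol*

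**What the plan says.** Section 5.1.1.5 of the protocol gives separate stop rules for cooling and for rewarming. Each phase has a short-duration list (5 to 10 minutes) and a longer one (more than 20 minutes).

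- **Saturation, short lists.** Both phases stop the cuddle at a saturation below 80%.
- **Saturation, cooling, more than 20 minutes.** The item is an absolute band, "Oxygen Saturation 80-88" (per cent), with no reference to the pre-cuddle value.
- **Saturation, rewarming, more than 20 minutes.** The same two numbers return with a comparison added: "Oxygen saturation 80-88% below the pre-CoolCuddle period".
- **Neighbouring rewarming items.** These are "Heart rate 30 beats per min above or below the pre-CoolCuddle period", "Mean Blood pressure 20mmHg above or below the pre-CoolCuddle period" and "Increase in Fraction of inspired oxygen by 20% above the pre-CoolCuddle period".
- **Temperature in rewarming.** The only item is "Rectal temperature greater than 4.0°C or less than 4.0°C from the pre-CoolCuddle period". The rewarming lists have no absolute temperature limit.
- **Catch-all in both phases.** "Medical or nursing concern that the infant is not adequately supported".

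Section 1 describes the planned temperature course: "body temperature is maintained at 33-34°C for three days followed by 6-8 hours of rewarming to normal temperature of 36.5°C".

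**The concern.** In the rewarming list, the items on either side of saturation state how far a measurement may move from its pre-cuddle value. The saturation item ends with the same comparison, so a reader going down the list would take it as a fall of 80 to 88. No infant would be allowed to reach that point. If the item cannot act, the band just above 80% has no numeric saturation rule in rewarming, although it has one in cooling.

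This is a bedside safety threshold, so its wording should have one meaning. It also touches the results. Section 4.2 counts use of the stop rules within the adverse-event outcome, and the Stage 2 data analysis treats a stopped cuddle as an adverse event.

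**Working it through.** The protocol gives no derived figure to reproduce. The check asks at what saturation the item would act under each possible reading, and compares that with the below-80% rule.

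**Inputs.** The band 80-88, the below-80% rule and the two durations come from section 5.1.1.5. The pre-cuddle saturation B is not given. I assume 88% to 100% and show 88%, 95% and 100%.

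| Reading | Formula | B = 100% | B = 95% | B = 88% |
|---|---|---|---|---|
| Fall in percentage points | B − 88 to B − 80 | 12 to 20% | 7 to 15% | 0 to 8% |
| Relative fall | B × 0.12 to B × 0.20 | 12 to 20% | 11.4 to 19.0% | 10.6 to 17.6% |
| Percentage of the pre-cuddle value | B × 0.80 to B × 0.88 | 80 to 88% | 76.0 to 83.6% | 70.4 to 77.4% |
| Absolute band, as in cooling | none | 80 to 88% | 80 to 88% | 80 to 88% |

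**Either fall reading.** The highest saturation at which the item could act is 100 − 80 = 20%. That lies below 80%, where the other rule acts after 5 to 10 minutes rather than after more than 20. The item is always pre-empted and adds nothing.

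**Percentage of the pre-cuddle value.** From 95% the item reaches only to 83.6%, so values above that up to 88% stay uncovered.

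**80-88% and lower than before.** For any pre-cuddle value above 88% this is the same as the absolute band. It sits directly above the below-80% rule and works.

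**What else could catch a saturation of 80-88%.** Extra oxygen might trip the inspired-oxygen rule. From an assumed 21%, a 20% increase is 21 + 20 = 41% in points, or 21 × 1.2 = 25.2% in relative terms; the protocol does not say which is meant. On a fall reading, an infant held at 80-88% with a smaller increase meets no numeric oxygenation rule.

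**Temperature query.** The planned rise is 36.5 − 34 = 2.5°C to 36.5 − 33 = 3.5°C. The 4.0°C limit is 4.0/3.5 = 1.1 to 4.0/2.5 = 1.6 times that whole rise. Taken as plus or minus 4.0°C, its upper trip point is 37.0 to 38.0°C from a start of 33 to 34°C. From 36.5°C the trip points are 40.5°C and 32.5°C. Taken literally, the wording covers almost any change.

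**The case against.** The strongest reply is that nobody at the cot-side would read the item as a fall of 80 points. The heart-rate and blood-pressure items give one magnitude and two directions, whereas this one gives a band and one direction, and the band is that of the cooling list. The section is loosely phrased elsewhere too: the temperature item has to be read generously to make sense, so strict literalism for saturation alone would be selective. This much stands. A workable reading exists, and it cannot be said that the item is certainly inert.

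It does not remove the point. The added comparison is the form used by the items around it, and it is absent from the cooling item. A threshold whose action depends on which reading staff choose needs correcting.

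A reader might infer that infants are unprotected in rewarming. The document does not support that. The rules for saturation below 80%, inspired oxygen, heart rate, blood pressure and status epilepticus remain, as does the clinical-concern rule. Nursing is one-to-one, and saturation is recorded every 5 minutes whether or not a rule is met, so the excursion would still be seen in the data.

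A reader might also infer that the slip will spread through the checklist or the published procedure. The checklist is not shown and the procedure is to be finalised in Stage 3, so copying is possible but not established.

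**Conclusion.** The item is mis-worded. On the reading that matches its neighbours it needs a saturation of 20% or less, is always pre-empted by the below-80% rule, and leaves a sustained 80-88% in rewarming without a numeric saturation stop. On the charitable reading it works. It is therefore at best ambiguous, and most probably a slip from the cooling list. The fall result does not depend on the assumed baseline, since 100% is the ceiling.

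The practical effect is probably small. The exposed case is an infant in rewarming who stays at 80-88%, whose inspired oxygen rises by too little to trip its own rule, and for whom staff raise no concern. The document does not allow the number of such cuddles, or any effect on stop-rule or adverse-event counts, to be estimated.

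A reader might go further and call the 4.0°C limit an error. The document does not show that. A wider band than in cooling is reasonable while temperature is being raised on purpose, the limit can act as a guard against overshoot from a cooled start, and the protocol offers no other value. That the limit exceeds the whole planned rise is a reason to ask whether it is intended, and no more.

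**What to change.** Restate the rewarming item as an absolute saturation of 80-88% lasting more than 20 minutes, in the words of the cooling list. Check the checklist, the case report form and any operating procedure that carries the stop rules, and correct them if they repeat the phrase.

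Separately, ask the clinical leads to reword the temperature item so that it plainly states a distance above or below the pre-cuddle value, and to confirm that 4.0°C is the limit they want.

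The cost is a one-phrase correction, one short clinical confirmation and a check of the forms, all within a single protocol amendment. No extra infants, procedures or data are needed.

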4.2 Outcomes

- Difference in mean/median and variability of surface and core temperature, ventilation, cardiovascular and neurophysiology parameters between the pre-cuddle, "CoolCuddle" and post cuddle epochs.
 - Day of life when oral feeds established
 - Mode and type of feeding at discharge and 8 weeks
 - Maternal mood assessed using Edinburgh postnatal depression scale¹ when the baby is 5-7 days of age and at 8 weeks.
 - Maternal-infant bonding assessed using Mother-infant bonding score³ when the baby is 5-7 days of age and at 8 weeks.
 - Father-infant attachment assessed using paternal postnatal attachment scale² at 8 weeks
 - Qualitative feedback on the "CoolCuddle" protocol
 - Incidence of adverse events including frequency of administering stop rules for "CoolCuddle", and dislodgement of endotracheal tube, central or peripheral arterial catheter, central venous catheter

5.STUDY DESIGN, METHODS OF DATA COLLECTION AND DATA ANALYSIS

This study will be a cohort study involving a controlled trial without randomisation design recruiting the cooled infants admitted to the NICUs of St Michael's and Southmead Hospital and their parents between September 2019 and January 2021.

5.1 Stage 1: Developing "CoolCuddle" protocol by refining existing cuddling technique using an iterative process (3 months)

Over 3 months, we will use the current family centred cuddling technique that we use for non-cooled babies receiving intensive care for babies receiving cooling treatment on 4-6 parents-infant pairs. We will attempt a minimum of one cuddle session per family up to 2 hours in length. We will refine the protocol by using 'talk-aloud' qualitative methods during each of the "CoolCuddle" sessions. Talk-aloud methods are used to gather data on usability and development of products and tasks³⁴. Talk-aloud methods involve participants describing their actions and how they go about completing the task. The audio-recordings made are used to improve the process through insights and modifications that arise during the session. A member of the research team will also observe all the "CoolCuddle" sessions and make field notes of changes made and actions taken.

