5.1.1.4 Moving the baby

The endotracheal tube and the ventilator circuits will be checked for any tangles. The nurse will stand at the bottom of the cot and support the baby's head and the cooling pillow with one hand and forearm approaching from the opposite side to the parents. The lower trunk and legs will be supported using the other arm with the infusion lines and the cables resting on the arm. When everyone is ready, the baby will be lifted from the bed maintaining the midline position. After a final check of the pathway of cables and lines ensuring there are no twists, the baby will be placed onto the parent's arms or on the lap or the top of a cushion/pillow (if used). If end-tidal carbon dioxide (CO2) monitoring is used, it will ascertain the patency of the endotracheal tube after transferring the baby onto the parent's arm or lap. Using the waveform morphology or the ventilator waveforms and air entry into the lungs will confirm

the endotracheal tube patency. The tubes from the cooling machine will be connected to the jacket to continue the cooling process. The cooling machine uses a servo control mechanism to maintain the set rectal temperature consistently²⁵. All monitoring of circulation and other physiological measures will be continued throughout the process as before the move. Once the baby is stable in the parent's arms, the baby will be turned to the side facing the parent maintaining the midline position. The Velcro straps that hold the infusion lines and the cables have a clip which will be clipped onto the parent's clothes.

The cuddle will continue for up to 2 hours but can be stopped earlier if the parent wishes or if any of the stop rules for cuddle are met. After the cuddle period, two nurses will move the baby back onto the cot following a similar process to that described above.

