We will have a 30-60 min pre-cuddle and post-cuddle epochs of data collection. A minimum of one cuddle episode per parents-infant pair during the four days of cooling therapy and rewarming period will be studied. Depending on the availability of nursing staff more frequent cuddle episodes will be encouraged. All cooled babies receive one to one nursing care in both the NICUs. An additional nurse is routinely involved in preparing drug infusions or delivering complicated care for babies receiving one-to-one nursing. Therefore, there will be no additional impact on the nursing workload.

Data collection

We will collect the demographic data of cooled infants and their parents, and maternal medical, social, pregnancy and labour history. The severity of encephalopathy, presence of multi-organ dysfunction, doses of drugs and continuous infusions received by the infant will be collected. During the precuddle, cuddle and post cuddle time periods the following physiology data will be collected on the case report form (CRF). Most of these data are stored digitally on the patient monitor every minute as part of routine care. These data can be used as a backup for the CRF and data at a sampling frequency of 1 minute can be obtained.

Physiology data

Date 11.02.2020 Version 1.6 CoolCuddle protocol

IRAS No. 257430

Every 5 minutes during pre-cuddle, cuddle and post-cuddle:

• Ventilation parameters: fraction of inspired oxygen, tidal volume, maximum peak inspiratory pressure, peak end expiratory pressure, mean airway pressure, inspiratory time, respiratory rate and oxygen saturation.

• Cardiovascular parameters: heart rate, blood pressure (the blood pressure transducer will be calibrated with the transducer at the level of the right atrium, every time the baby is moved)

• Surface and rectal temperature.

Other data to be collected

• End-tidal CO2 (if used in the NICU). Blood gas (measuring blood pH, pO2, pCO2, lactate, glucose) in the pre and post cuddle epoch. Blood gas is performed to ensure the babies are stable before and after cuddle in terms of oxygenation, ventilation and blood sugar. This is part of the standard care when babies are moved out of the incubator for longer periods.

• aEEG and NIRS (if used on the babies) will be marked at the onset of pre-cuddle, cuddle and post cuddle. aEEG will be analysed offline for continuity and seizures. NIRS data will be entered every 5 mins in the CRF.

- Adverse events

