The physiology data collection will be similar to stage 1; frequency and duration of data collection will be informed by the learning from the stage 1. The physiology data will be collected in the CRF and stored in the electronic databases. The questionnaire data including the responses from the EPDS, MIBS and paternal postnatal attachment scale will be stored in a REDCap database.

Data including the reasons parents did not want to consent for the study or cut short the cuddling episodes will be recorded.

The qualitative interviews will be audio-recorded, transcribed and anonymised.

Data Analysis

We will use descriptive statistics to report the parental questionnaire data and the adverse events. We will measure the mean or median (as appropriate) for the main physiological measures (see above). We will undertake three pairwise comparisons of pre-cuddle versus during-cuddle, during-cuddle versus post-cuddle and pre-cuddle versus post-cuddle using parametric t test or non-parametric Wilcoxon tests depending on the data distribution. We will derive the differences between the three

Date 11.02.2020 Version 1.6

23 of 37

IRAS No. 257430 CoolCuddle protocol

epochs (pre-cuddle, cuddle, and post-cuddle) and identify the magnitude of the differences, or variability which occurs. Using multilevel mixed-effects linear regression models, using data clustered by infant (or cuddle), we will assess if any difference in measures is likely to be due to chance (using a conventional level of statistical significance of p<0.05). We will also explore continuous monitoring of the physiological measures to establish variability over longer periods and the potential for adverse events. All data analysis will be conducted using the software SPSS or STATA.

We will compare our findings from the parental questionnaires with normative data. To compare parental bonding, we will collect these scores in our study to ensure they are in the satisfactory range following the "CoolCuddle". There are published normative data for mother-infant bonding scores³ and cut-offs for the father-infant attachment scores². We will compare our scores against these published data. We will also have detailed audit data on breastfeeding initiation and duration before September 2019 to compare with our study findings. If the cuddling process is stopped this will be treated as an adverse event and fully investigated to realise whether the problem is endemic, or modifiable and preventable.

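### Rewarming-phase cuddles enter the same raw pre/during/post temperature comparison as cooling-phase cuddles, so the planned rise to 36.5°C biases the epoch differences for those episodes

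*Protocol*

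**What the plan says.** **Which episodes are studied.** The text after the stop rules in section 5.1.1.5 reads: "A minimum of one cuddle episode per parents-infant pair during the four days of cooling therapy and rewarming period will be studied". Rewarming cuddles are foreseen explicitly: "If cuddle is undertaken during the rewarming period, the following stop rules will apply". That second set of limits is wider than the cooling set for the change from the pre-cuddle value in heart rate (30 instead of 20 beats/min) and in mean blood pressure (20 instead of 10 mmHg). Its temperature limit is also different in kind: "Rectal temperature greater than 4.0°C or less than 4.0°C from the pre-CoolCuddle period".

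**What temperature does in each phase.** Section 1 states that "body temperature is maintained at 33-34°C for three days followed by 6-8 hours of rewarming to normal temperature of 36.5°C".

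**The outcome and the epochs.** Section 4.2 lists "Difference in mean/median and variability of surface and core temperature, ventilation, cardiovascular and neurophysiology parameters between the pre-cuddle", cuddle and post-cuddle epochs. On timing: "We will have a 30-60 min pre-cuddle and post-cuddle epochs of data collection" (after section 5.1.1.5) and "The cuddle will continue for up to 2 hours" (section 5.1.1.4).

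**The analysis.** Section 5, Stage 2, Data Analysis plans "three pairwise comparisons of pre-cuddle versus during-cuddle, during-cuddle versus post-cuddle and pre-cuddle versus post-cuddle" by t test or Wilcoxon test. It adds multilevel linear models with data clustered by infant or cuddle, judged at p<0.05. It does not mention treatment phase or time since the start of rewarming, and nothing in the protocol removes rewarming episodes from these comparisons.

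**The purpose.** Section 3 says the comparison of epochs is meant to assess short-term safety while the baby is being cooled. The flow chart (Fig 1) places the Stage 1 minimum of one cuddle in the cooling period, whereas the sentence quoted first above lets that minimum fall in either phase.

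**The concern.** Pre, during and post always run in that order in time. In the cooling phase the target temperature is constant, so a difference between epochs can be put down to the move and the cuddle, plus noise. In rewarming the target itself moves upward through all three epochs. The raw difference between epochs then contains the planned rise as well as any cuddle effect, and a comparison of epoch means cannot tell them apart.

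Three results are exposed:

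- **Mean temperature.** A rewarming episode shows a rise that has nothing to do with being held. If a cuddle did lower temperature, the rise would offset the fall and could hide it.
- **Variability**, which section 4.2 names as an outcome in its own right. A steady drift widens the spread of readings within an epoch, and widens it more in the longer cuddle epoch.
- **Heart rate and blood pressure**, possibly. The wider rewarming limits suggest that the authors expect these to move as well, but the protocol gives no figures from which to size that.

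Physiological change feeds the traffic-light decision in section 3, where adverse physiological changes put the study in the orange zone. The protocol recognises the phase difference in its stop limits but does not carry it into the analysis.

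**Working it through.** The protocol gives no power, effect size or SD for temperature, so it has no figure of its own to reproduce on this point.

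**1. Rate of planned rise.** Inputs from section 1: start 33-34°C, end 36.5°C, duration 6-8 h. The rise is 36.5 − 34 = 2.5°C to 36.5 − 33 = 3.5°C. Assuming it is linear:
- slowest: 2.5/8 = 0.31°C/h
- fastest: 3.5/6 = 0.58°C/h

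**2. Drift between epoch means, no cuddle effect.** Let E be the length of each flanking epoch (0.5-1 h) and C the cuddle length. Epoch midpoints are (E + C)/2 apart for pre-during and for during-post, and E + C apart for pre-post. Drift = rate × gap, for an episode wholly inside rewarming.

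| Cuddle | Pre-during | Pre-post |
|---|---|---|
| 2 h (maximum) | 0.3125 × 1.25 = 0.39 to 0.583 × 1.5 = 0.88°C | 0.3125 × 2.5 = 0.78 to 0.583 × 3 = 1.75°C |
| 30 min | 0.3125 × 0.5 = 0.16 to 0.583 × 0.75 = 0.44°C | 0.3125 × 1 = 0.31 to 0.583 × 1.5 = 0.88°C |

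For scale, the cooling target band of 33-34°C is 1°C wide.

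**3. Within-epoch spread from drift alone.** For a linear drift over length L, SD = rate × L/√12.
- 2 h cuddle: 0.3125 × 2/3.464 = 0.18 to 0.583 × 2/3.464 = 0.34°C
- 30-60 min flanking epoch: 0.3125 × 0.5/3.464 = 0.05 to 0.583 × 1/3.464 = 0.17°C

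**4. How many episodes might be affected.** The protocol gives no number. Rewarming takes 6 of 78 h to 8 of 80 h, i.e. 7.7-10% of the treatment time. If cuddles were spread evenly, that is 24 × 0.077 = 1.8 to 24 × 0.10 = 2.4 of 24 episodes.

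**5. Pooled shift and false-positive rate.** With one episode per infant, pooled shift = (k/24) × drift for k rewarming episodes. Rejection rates come from 10,000 simulated paired two-sided t tests at 0.05 with no true effect, a 2 h cuddle and an assumed SD of paired differences of 0.2°C.

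| k of 24 | Pre-during shift | Rejects | Pre-post shift | Rejects |
|---|---|---|---|---|
| 0 | 0 | about 5% | 0 | about 5% |
| 2 | 0.03-0.07°C | 7-8% | 0.07-0.15°C | 4-9% |
| 6 | 0.10-0.22°C | 38-79% | 0.20-0.44°C | 73-99% |
| 12 | 0.20-0.44°C | 96-100% | 0.39-0.88°C | 100% |

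At k = 6, varying the SD over 0.1-0.3°C gives 24-99% (pre-during) and 52-100% (pre-post). The Wilcoxon test is less sensitive: at k = 6 and SD 0.2°C it rejects in 29-45% and 41-46% (300 runs).

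At k = 2 the t test stays near nominal for a poor reason: the few large values inflate the SD as well as shifting the mean.

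**6. The mixed model.** The protocol assigns the judgement of chance to this model but does not say whether it uses the 5-minute readings or epoch means. A random-intercept model on the readings (2 h cuddle, independent residuals with SD 0.1-0.3°C, both assumed) rejected in 22-100% (pre-during) and 43-100% (pre-post) of runs at k = 2, against 4-7% at k = 0. Real readings are serially correlated, so this shows sensitivity to the choice of unit and is not a forecast.

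**The case against.** The strongest reply is that pooling is inferred. The Data Analysis text does not say in so many words that all episodes are combined, an unseen SAP could stratify by phase, and sections 3 and 7.3.2 and the flow chart all point to the cooling period. Phase must be known at the bedside to choose the stop limits, so episodes could be classified afterwards. Part of this stands: the remedy is easy, and a SAP may already contain it. It does not remove the point. The protocol itself fixes the eligible episodes, the tests, the model and the significance level, and excludes no rewarming episode. Followed as written, it gives a biased comparison.

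The second reply concerns size, and most of it stands. Two hours is the maximum cuddle length. The full drift requires the whole 3-4 h span to lie inside a 6-8 h ramp. With evenly spread start times (assumed), that leaves a window of 6 − 4 = 2 h to 8 − 3 = 5 h out of 78-80 h, about 3-6% of episodes; straddling episodes drift less.

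A reader might therefore infer too much in three ways:

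- **That the rise will be reported as a cuddle effect.** This depends on the number of rewarming cuddles. No passage suggests as many as 6 of 24.
- **That epoch and rewarming are inseparable in the data.** Raw epoch means are biased, but readings every 5 minutes could separate a step at the start or end of a cuddle from a steady ramp, if the analysis modelled it.
- **That the progression decision would turn on it.** The traffic-light rule rests on adverse effects, whether they are modifiable, and discussion with the steering committee. It is not tied to a pooled p-value.

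**Conclusion.** The point holds at moderate severity. The protocol admits rewarming cuddles, separates their stop limits, and then analyses raw epoch differences without regard to phase, although the stated purpose is safety during cooling.

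For a single episode wholly inside rewarming the bias is large: +0.39 to +0.88°C pre to during and +0.78 to +1.75°C pre to post at 2 h, and still +0.16 to +0.44°C and +0.31 to +0.88°C at 30 min. These figures use only the protocol's own numbers and a linear rise. Within-epoch variability is inflated as well, and a real fall can be masked.

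The effect on the pooled result cannot be settled from the protocol. It is small at about 2 of 24 episodes and substantial at 6 of 24. Those pooled significance rates rest on an assumed SD and one episode per infant. The documents do not support saying that the main result will be wrong, so this is not a defect that must stop the study.

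**What to change.** In section 5, Stage 2, Data Analysis:

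1. Classify each episode as cooling, rewarming or straddling, from the recorded start of rewarming.
2. Make cooling-phase episodes the main pre/during/post physiological comparison. With no rewarming episodes included, the simulated t-test false-positive rate is 4.7-5.3%.
3. Report rewarming and straddling episodes separately, with temperature expressed at each reading as the deviation from the planned rewarming course, or from the device set point where that is recorded.
4. Reconcile section 3, the flow chart and the text after section 5.1.1.5 on which phase the studied cuddles belong to.

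A phase term with a time trend in the mixed model would be a workable alternative to step 2, but the few rewarming episodes expected would support it poorly.

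**Cost.** The start time of rewarming must be recorded, and an infant cuddled only in rewarming does not contribute to the main comparison. The intervention, the stop limits and the sample size need not change for this purpose, and no view is taken here on the stop limits. If no rewarming cuddles occur, nothing is lost.
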